9.4. Data sources

There will be several sources of information. From the medical record provided by the patient will be abstracted the demographic and clinical characteristics related to diagnosis, comorbidities, and treatment at baseline, as well as the previous medications to manage CA. Other sources will be the patient to confirm or complete the information associated with it.

During the follow-up, the patient will provide the information about changes in the treatment, issues to supply tafamidis, and hospitalization which be confirmed with the summary of the medical records of the patient. The quality of life will be measured using the KCCQ scale through call or face to face meetings. 6-MWT and scintigraphy will be abstracted from medical records.

Adherence will be measured using the information available in the Popit sense device. It is only available in patients that use this device. If the patient does not have access to Popit, it will not be a limitation to participate in the study, only that this variable will be not measured for them. These scales have been validated (12) and translated to Spanish of Colombia (14).

PFIZER CONFIDENTIAL

CT24-WI-GL02-RF01 6.0 Non-Interventional Study Protocol Template For Primary Data Collection Study 01-

Aug-2023

Page 30 of 57

CLINICAL AND MEDICAL CONTROLLED DOCUMENT (CMCD) REQUIRED FORM/TEMPLATE

Identifier	Version	Title	Effective Date
CT24-WI-GL02-RF01	6.0	NON-INTERVENTIONAL STUDY PROTOCOL TEMPLATE FOR PRIMARY DATA COLLECTION STUDY	01-Aug-2023

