9.3. Variables

Table 2 List of variables

Variable	Role	Data source(s)	Operational definition
Date of birth	Demographic characteristics	Medical record, Interview	dd-mm-yyyy
Age	Demographic characteristics	Medical record, Interview	Time elapsed since the time of birth to signed consent form (years)
Sex assigned at birth	Demographic characteristics	Medical record, Interview	Men, female
Race (ethnicity)	Demographic characteristics	Medical record, Interview	Indigenous, Rrom, Black, None and Other
Date of symptoms of ATTR-CM	Clinical characteristic	Medical record, Interview	dd-mm-yyyy
Date of ATTR-CM diagnosis	Clinical characteristic	Medical record, Interview	dd-mm-yyyy
Genotype	Clinical characteristic	Medical record, Interview	ATTRwt; ATTRv
Scintigraphy at diagnosis (Perugini scale)	Clinical characteristic	Medical record,	Grade 0 – 3
Biopsy	Clinical characteristic	Medical record, Interview	Yes, No
Sampling biopsy	Clinical characteristic	Medical record, Interview	Heart, bone marrow, others
Sum of QRS amplitude in I, II, and III leads at diagnosis	Clinical characteristic	Medical record, Interview	mm
Sum of QRS amplitude in all six limb leads at diagnosis	Clinical characteristic	Medical record, Interview	mm
Sum of QRS amplitude in all six precordial leads at diagnosis	Clinical characteristic	Medical record, Interview	mm
Sokolow-Lyon index low voltage criteria at diagnosis	Clinical characteristic	Medical record, Interview	mm
Low QRS voltage at diagnosis	Clinical characteristic	Medical record, Interview	Yes, No

PFIZER CONFIDENTIAL

CT24-WI-GL02-RF01 6.0 Non-Interventional Study Protocol Template For Primary Data Collection Study 01-

Aug-2023

Page 24 of 57

**CLINICAL AND MEDICAL CONTROLLED DOCUMENT (CMCD)
REQUIRED FORM/TEMPLATE**

Identifier	Version	Title	Effective Date
CT24-WI-GL02-RF01	6.0	NON-INTERVENTIONAL STUDY PROTOCOL TEMPLATE FOR PRIMARY DATA COLLECTION STUDY	01-Aug-2023

Pseudo-infarct Q waves at diagnosis	Clinical characteristic	Medical record, Interview	Yes, No
Atrioventricular conduction disease (block) at diagnosis	Clinical characteristic	Medical record, Interview	Yes, No
Genetic counseling	Patient	Medical record, Interview	Yes, No
Left ventricular ejection fraction at diagnosis	Clinical characteristic	Medical record, Interview	%
N-terminal pro b-type natriuretic peptide at diagnosis	Clinical characteristic	Medical record, Interview	(pg/mL)
Heart failure at early age	Clinical characteristic	Medical record, Interview	Yes, No

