Erectile dysfunction	Clinical characteristic	Medical record, Interview	Yes, No
Glaucoma	Clinical characteristic	Medical record, Interview	Yes, No
Intravitreal deposition	Clinical characteristic	Medical record, Interview	Yes, No
angiotensin-converting enzyme inhibitors previous diagnosis	Treatment	Medical record, Interview	Yes, No
Agents acting on the renin-angiotensin system previous diagnosis	Treatment	Medical record, Interview	Yes, No
HMG COA reductase inhibitors previous diagnosis	Treatment	Medical record, Interview	Yes, No
Loop diuretics previous diagnosis	Treatment	Medical record, Interview	Yes, No
Amiodarone previous diagnosis	Treatment	Medical record, Interview	Yes, No

PFIZER CONFIDENTIAL

CT24-WI-GL02-RF01 6.0 Non-Interventional Study Protocol Template For Primary Data Collection Study 01-

Aug-2023

Page 26 of 57

**CLINICAL AND MEDICAL CONTROLLED DOCUMENT (CMCD)
REQUIRED FORM/TEMPLATE**

Identifier	Version	Title	Effective Date
CT24-WI-GL02-RF01	6.0	NON-INTERVENTIONAL STUDY PROTOCOL TEMPLATE FOR PRIMARY DATA COLLECTION STUDY	01-Aug-2023

Anticoagulation previous diagnosis	Treatment	Medical record, Interview	Yes, No
Beta blockers previous diagnosis	Treatment	Medical record, Interview	Yes, No
Calcium channel blockers previous diagnosis	Treatment	Medical record, Interview	Yes, No
Angiotensin receptor blockers previous diagnosis	Treatment	Medical record, Interview	Yes, No
Agents acting on the renin–angiotensin system after diagnosis*	Treatment	Medical record, Interview	Yes, No
HMG COA reductase inhibitors after diagnosis*	Treatment	Medical record, Interview	Yes, No
Loop diuretics after diagnosis *	Treatment	Medical record, Interview	Yes, No
Amiodarone after diagnosis*	Treatment	Medical record, Interview	Yes, No
Anticoagulation after diagnosis *	Treatment	Medical record, Interview	Apixaban, dabigatran, rivaroxaban, warfarin
Beta blockers after diagnosis*	Treatment	Medical record, Interview	Yes, No
Calcium channel blockers after diagnosis*	Treatment	Medical record, Interview	Yes, No
Angiotensin receptor blockers after diagnosis*	Treatment	Medical record, Interview	Yes, No
angiotensin-converting enzyme inhibitors previous diagnosis*	Treatment	Medical record, Interview	Yes, No
Glomerular filtration rate at diagnosis*	Clinical characteristics	Medical record, Interview	>40, <40

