Cardiovascular devices during follow-up	Treatment	Medical record, Interview	Cardiac resynchronization therapy – defibrillator (CRT-D), Cardiac resynchronization therapy – pacemakers (CRT-P), implantable cardioverter defibrillator (ICD)
Date of prescription of tafamidis	Treatment	Interview	ddmm/yyyy

PFIZER CONFIDENTIAL

CT24-WI-GL02-RF01 6.0 Non-Interventional Study Protocol Template For Primary Data Collection Study 01-

Aug-2023

Page 27 of 57

**CLINICAL AND MEDICAL CONTROLLED DOCUMENT (CMCD)
REQUIRED FORM/TEMPLATE**

Identifier	Version	Title	Effective Date
CT24-WI-GL02-RF01	6.0	NON-INTERVENTIONAL STUDY PROTOCOL TEMPLATE FOR PRIMARY DATA COLLECTION STUDY	01-Aug-2023

Date of first administration of tafamidis	Treatment	Interview	ddmm/yyyy
Delay of supply of tafamidis	Treatment	Interview	Yes, No
Cause of delay	Treatment	Interview	Authorization, Treatment not available in the supplier, error of prescription, other
Adherence	Outcomes	Interview	%
Sum of QRS amplitude in I, II, and III leads at the end of follow-up	Clinical characteristic	Medical record, Interview	mm
Sum of QRS amplitude in all six limb leads at the end of follow-up	Clinical characteristic	Medical record, Interview	mm
Sum of QRS amplitude in all six precordial leads at the end of follow-up	Clinical characteristic	Medical record, Interview	mm
Sokolow-Lyon index low voltage criteria at the end of follow-up	Clinical characteristic	Medical record, Interview	mm
Persistence	Outcomes	Interview	Yes, No
Hospitalization	Outcomes	Interview	Yes, No
Cause of the hospitalization	Outcomes	Interview	Cardiovascular, Other
Date of hospitalization	Outcomes	Interview	Date of admission: dd-mm-yyyy Date of discharge: dd-mm-yyyy
Day(s) of hospitalization	Outcomes	Interview	Days
Quality of life (KCCQ-OS score per visit)	Outcomes	Interview	Score
6MWT [§]	Outcomes	Site	Meters
Scintigraphy (Perugini scale) [§]	Outcomes	Site	Grade 0 - 3

* Per visits, according to schedule of the study

§ According to medical criteria, considering that the physician may choose to perform a different test

PFIZER CONFIDENTIAL

CT24-WI-GL02-RF01 6.0 Non-Interventional Study Protocol Template For Primary Data Collection Study 01-

Aug-2023

Page 28 of 57

**CLINICAL AND MEDICAL CONTROLLED DOCUMENT (CMCD)
REQUIRED FORM/TEMPLATE**

Identifier	Version	Title	Effective Date
CT24-WI-GL02-RF01	6.0	NON-INTERVENTIONAL STUDY PROTOCOL TEMPLATE FOR PRIMARY DATA COLLECTION STUDY	01-Aug-2023

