9.7.4. Handling of Missing Data

There will be no imputation or replacement of missing data. All analyses will be conducted on observed cases. All patients will be included in the descriptive analysis limited with the information recollect. The missing data will be included in the study report. Analysis with case complete will not be conducted.

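### Table 2 accepts the patient interview as a source for ECG voltages, LVEF, NT-proBNP and the GFR category; these rows should rest on documented results only

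*Protocol*

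**What the plan says.** Table 2 in Protocol section 9.3 has a source column. For rows that can only come from an instrument or a laboratory, that column names both the medical record and the interview. One ECG row reads "Sum of QRS amplitude in I, II, and III leads at diagnosis Clinical characteristic Medical record, Interview mm", and its counterpart at the end of the study reads "Sum of QRS amplitude in I, II, and III leads at the end of follow-up Clinical characteristic Medical record, Interview mm". The same pair of sources stands against "Sokolow-Lyon index low voltage criteria at the end of follow-up", "Left ventricular ejection fraction at diagnosis", "N-terminal pro b-type natriuretic peptide at diagnosis" and "Glomerular filtration rate at diagnosis".

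Section 9.4 describes how the two sources work together at baseline. Data on diagnosis, comorbidity and treatment are taken from the medical record that the patient provides, and then: "Other sources will be the patient to confirm or complete the information associated with it".

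Two places point the other way. Table 2 lists scintigraphy at diagnosis with the medical record alone, and section 9.4 takes the 6-minute walk test and scintigraphy from medical records. Section 9.1 says that baseline clinical information comes from the medical record. However, 9.1 also says that for patients prescribed before the study began, earlier information is collected from data that the patients provide.

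**The concern.** A patient can report symptoms, history and medication. A summed QRS amplitude in millimetres, an ejection fraction or an NT-proBNP concentration is different: without a document behind it, nobody can check it. The plan lets the interview fill exactly these fields when the record is silent.

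Gaps in the record are foreseeable. Under section 9.2, patients may be referred from institutions outside the study, stay in care there and be interviewed virtually, so a site may hold only the papers that the patient brings.

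The values are used in three ways. They describe the cohort at prescription (first secondary objective), clinical characteristics define subgroups (9.7.3.2), and baseline characteristics enter the exploratory regressions if numbers allow (9.7.5.2). An undocumented value in any of these adds measurement error and makes the data look more complete than the records are.

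**Working it through.** The protocol gives no figure for this point, so the check sets its sections side by side and adds two small calculations.

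**1. Rows affected (Table 2).**
- ECG voltages at diagnosis: leads I to III, six limb leads, six precordial leads, Sokolow-Lyon index = 4
- The same four at end of follow-up = 4
- Low QRS voltage and pseudo-infarct Q waves at diagnosis = 2
- LVEF (%) and NT-proBNP (pg/mL) at diagnosis = 2
- GFR at diagnosis, recorded only as above or below 40 = 1

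Total: 4 + 4 + 2 + 2 + 1 = 13 rows, of which 13 − 4 = 9 refer to diagnosis.

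**2. Which rule governs each group.** For the nine rows at diagnosis, Table 2 names the interview as a source and 9.4 lets the patient supply what the record lacks. For the four end-of-follow-up ECG rows, only the source column gives the permission, because the 9.4 sentence concerns baseline data.

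**3. Are the sections consistent?** No.
- Table 2 and 9.4 allow the interview for the nine rows at diagnosis.
- One sentence of 9.1 points to the record for baseline clinical data.
- Another sentence of 9.1 points to data from the patient when prescription came before the study.

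That second sentence covers the whole planned cohort. Prescription falls no later than August 2023 (9.1, 9.2), and data collection starts on 15 November 2023 (section 6).

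**4. Least time between diagnosis and interview.** Assume that diagnosis comes no later than prescription. From 31 August to 15 November 2023 is 30 + 31 + 15 = 76 days. From 1 August 2022, the start of the recruitment window, it is 365 + 106 = 471 days, or about 15 months. So the value at diagnosis is at least two and a half months old at the first possible interview. The protocol gives no time from diagnosis to prescription, so nothing longer can be claimed.

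**5. What happens to an interview value in the analysis.** Section 9.7.4 analyses observed cases. An interview value comes from a permitted source, so it counts as observed. Section 9.7 describes no separate treatment by source.

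**6. Weight of one value.** Section 9.5 expects close to fifty patients and 9.2 fewer than 50. One value is therefore about 1/50 = 2% of a row, or slightly more.

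**The case against.** The strongest reply is that nothing in the protocol says that recalled numbers will be used. The record reaches the site through the patient, so completing the data may simply mean handing over another report. A summed six-lead amplitude is an implausible thing to recall, and a blank is the likelier result. This stands: the text permits undocumented values but does not show that they occur. Because it permits them, the wording still needs tightening.

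A reader might also infer that such values are mixed with measured ones unmarked. That rests on silence. Table 2 lists no source variable, but it is not the CRF, and neither the CRF nor the monitoring plan is shown.

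A reader might further see a clash with 9.7.4, which states "There will be no imputation or replacement of missing data". There is none. That rule concerns the analysis, and a value collected at interview is data, not imputation.

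Safeguards exist. Section 9.6.1 requires CRF entries to match the chart where the chart is the source, and a document listing the data for which the CRF is itself the source. Section 9.8 plans three monitoring rounds against the sources, plus outlier checks and queries. Section 9.9 admits that baseline information depends partly on what the patient knows. These lower the risk and disclose it. They do not close the gap, because a value whose only source is the interview has no chart entry to be matched against.

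**Conclusion.** The point holds as a minor defect in a rule that the protocol itself states. Table 2 and 9.4 permit undocumented, patient-reported test results for 13 rows, out of step with the record-only treatment of scintigraphy at diagnosis and with one sentence of 9.1.

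The reach is limited. The nine rows at diagnosis bear on the baseline description, the subgroups and the exploratory models. The four end-of-follow-up ECG rows are not baseline predictors and do not belong to the first secondary objective. For GFR, the risk is a wrong category, not a wrong number. The primary KCCQ outcome is patient-reported by design and is untouched.

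No bias can be quantified. It is tempting to assume that some share of values is pure noise and to compute the resulting weakening of a regression slope. The protocol gives no such share, and a single-predictor result would not carry over directly to the multivariable mixed models or to a two-level GFR. The conclusion rests only on the wording of Table 2, 9.1 and 9.4, and on sites following it as written.

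**What to change.** - In Table 2, set the source of the 13 rows to the medical record only. Define this to include a report or record that the patient provides.
- State that the value is left missing if no document supports it.
- Reword 9.4 so that completion by the patient covers symptoms, history and medication but not test results.
- Bring both sentences of 9.1 into line with this.
- Optional: add a record/interview indicator to the CRF for the rows that keep both sources. It has to be set at data entry, because the origin of a value is hard to reconstruct later.

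The cost is a few cell edits and two reworded paragraphs, plus one CRF field if the indicator is adopted. The reported missing-data rate for these rows will rise, but it will then show what the records actually contain.

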9.5. Study size

Sample size is not required for being observational and descriptive study. The expected number of patients eligible for the study is close to fifty considering the number of patients identified with the diagnosis and the access to the treatment based on the national database of MiPres in Colombia in which each prescription of treatments outside of National Formulary must be registered (19).

9.6. Data management

9.6.1. Case report forms (CRFs) /Data Collection Tools (DCTs)/Electronic Data Record

As used in this protocol, the term CRF should be understood to refer to either a paper form or an electronic data record or both, depending on the data collection method used in this study.

A CRF is required and should be completed for each patient included. The completed original CRFs are the sole property of Pfizer and should not be made available in any form to third parties, except for authorized representatives of Pfizer or appropriate regulatory authorities, without written permission from Pfizer. The investigator shall ensure that the CRFs are securely stored at the study site in encrypted electronic and/or paper form and will be password protected or secured in a locked room to prevent access by unauthorized third parties.

The investigator has ultimate responsibility for the collection and reporting of all clinical, safety, and laboratory data entered on the CRFs and any other data collection forms (source documents) and ensuring that they are accurate, authentic/original, attributable, complete, consistent, legible, timely (contemporaneous), enduring, and available when required. The CRFs must be signed by the investigator or by an authorized staff member to attest that the data contained on the CRFs are true. Any corrections to entries made in the CRFs or source documents must be dated, initiated, and explained (if necessary) and should not obscure the original entry.

In most cases the source documents are the hospital or the physician's chart. In these cases, data collected on the CRFs must match those charts.

In some cases, the CRF may also serve as the source document. In these cases, a document should be available at the investigator site and at Pfizer that clearly identifies those data that will be recorded on the CRF, and for which the CRF will stand as the source document.

9.6.2. Record retention

To enable evaluations and/or inspections/audits from regulatory authorities or Pfizer, the investigator agrees to keep records, including the identity of all participating patients (sufficient information to link records, e.g., CRFs and hospital records), all original signed informed consent documents, copies of all CRFs, safety reporting forms, source documents, detailed records of treatment disposition, and adequate documentation of relevant correspondence (e.g., letters, meeting minutes, and telephone call reports). The records should

PFIZER CONFIDENTIAL

CT24-WI-GL02-RF01 6.0 Non-Interventional Study Protocol Template For Primary Data Collection Study 01-

Aug-2023

Page 31 of 57

CLINICAL AND MEDICAL CONTROLLED DOCUMENT (CMCD) REQUIRED FORM/TEMPLATE

Identifier	Version	Title	Effective Date
CT24-WI-GL02-RF01	6.0	NON-INTERVENTIONAL STUDY PROTOCOL TEMPLATE FOR PRIMARY DATA COLLECTION STUDY	01-Aug-2023

be retained by the investigator according to local regulations or as specified in the clinical study agreement (CSA), whichever is longer. The investigator must ensure that the records continue to be stored securely for so long as they are retained.

If the investigator becomes unable for any reason to continue to retain study records for the required period (e.g., retirement, relocation), Pfizer should be prospectively notified. The study records must be transferred to a designee acceptable to Pfizer, such as another investigator, another institution, or to an independent third party arranged by Pfizer.

Study records must be kept for a minimum of 15 years after completion or discontinuation of the study or as required by applicable local regulations.

The investigator must obtain Pfizer's written permission before disposing of any records, even if retention requirements have been met.

9.7. Data analysis

9.7.1. Statistical Hypotheses

This is a descriptive, prospective, and observational study. There is no formal hypothesis being tested. The study will describe the clinical and demographic characteristics of ATTR-CM patients. Also, it will describe previous treatments, cardiovascular devices, and comorbidities.

Adherence, persistence, and frequency of hospitalization will be described during the time exposure of treatment.

The change of baseline in the quality of life measured every 3 and 6 months respectively for 24 months.

9.7.2. Statistical Decision Rules

Given that no hypotheses are tested, a – priori defined statistical decision rules are not applicable.

9.7.3. Population Analysis

9.7.3.1. Total population

The analyses will be conducted for all the eligible patients.

9.7.3.2. Subgroup analysis

Analyses will be performed for the following sub-groups:

- Age
- Sex assigned at birth
- Genotype of ATTR-CM
- Scintigraphy at diagnosis

PFIZER CONFIDENTIAL

CT24-WI-GL02-RF01 6.0 Non-Interventional Study Protocol Template For Primary Data Collection Study 01-

Aug-2023

Page 32 of 57

CLINICAL AND MEDICAL CONTROLLED DOCUMENT (CMCD) REQUIRED FORM/TEMPLATE

Identifier	Version	Title	Effective Date
CT24-WI-GL02-RF01	6.0	NON-INTERVENTIONAL STUDY PROTOCOL TEMPLATE FOR PRIMARY DATA COLLECTION STUDY	01-Aug-2023

- Clinical characteristics
- Comorbidities
- Cardiovascular devices NYHA at start of tafamidis
- Any delay of supply (Yes or No)
- Time of treatment with tafamidis (Interval between date of diagnosis to date of start treatment with tafamidis)
- Time with tafamidis before enrollment in the study

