9. RESEARCH METHODS

9.1. Study design

The study will be a non-interventional, descriptive, and longitudinal prospective study with primary data collection that involves sites/investigators. The patients must be diagnosed before enrollment with ATTR-CM and prescribed with tafamidis following indications approved by National Institute for Drug and Food Vigilance (INVIMA) in Colombia. The patients will be followed up from the index date until patient i) have deceased, ii) have decided to withdraw from the study, iii) have terminated of treatment, iv) have been lost to follow up, or, v) finalize the 24 months of following up, the event that happens first. The index date will be defined as the date for the first prescription of tafamidis.

The patients that were prescribed with tafamidis before August of 2023 will be recruited. In the cases where the patients were prescribed before starting the study, all previous information will be collected from the data provided by the patients. The quality of life will be evaluated when the patient accepts to participate and signs the informed consent.

Quality of life, adherence, concomitant treatment, hospitalization for any causes, cardiovascular functionality will be measured 24 months after the prescription of tafamidis. Twelve months before the index date, treatments, and frequency of hospitalization for any causes will be measured (Table 1).

There will be two sources of information. Clinical and demographic information and death at the baseline will be abstracted from the medical record while the data related to hospitalizations, cardiovascular functionality, quality of life will be collected directly from the patients using validated questionnaires and structured interviews. Thus, in this case the report form (CRF) will serve as a source document.

In patients who have been prescribed with tafamidis more than 1 month and have not received the drug by the HMO yet, the first time of administration of tafamidis will be considered in the analysis. It will be considered as limitation of access. Any delay of supply for treatment will be considered limitation of access which will be assessed during the follow-up.

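### The any-delay subgroup has no time point: if the label builds up over follow-up, the Yes group over-represents patients observed longest

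*Protocol*

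**What the plan says.** Describing access barriers during tafamidis use is a secondary objective (Protocol, section 8). The relevant provisions are:

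- **Section 9.1** singles out one situation, "In patients who have been prescribed with tafamidis more than 1 month and have not received the drug by the HMO yet", and treats it as limited access. It then adds a broader rule: "Any delay of supply for treatment will be considered limitation of access which will be assessed during the follow-up".
- **Section 9.3, Table 2** has a row "Delay of supply of tafamidis", answered Yes or No at interview, and one cause field with the options "Authorization, Treatment not available in the supplier, error of prescription, other". Neither has a date, a length or a count. Table 2 separately records "Date of prescription of tafamidis" and the date of first administration, and section 9.1 says the analysis will take both dates into account.
- **Section 9.4** has patients report supply problems during follow-up.
- **Section 9.7.3.2** lists "Any delay of supply (Yes or No" among the subgroups, with no time point. Section 9.7.5.1 foresees comparing means or medians between subgroups.
- **Section 9.1** ends follow-up at the first of death, withdrawal from the study, end of treatment, loss to follow-up or 24 months.
- **Section 9.3.1** (Persistence) places discontinuation at the point where the previous prescription's supply runs out.

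**The concern.** A subgroup should be fixed by something known before the outcomes it is compared on. Read with section 9.1, this one appears to depend on events after the index date. A patient who dies or stops treatment at month 6 has had two 3-month intervals in which a delay could occur; one who completes has had eight. The first is therefore more likely to end in the No group for that reason alone. This is immortal-time bias.

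The direction of the error depends on the outcome. A longer-observed Yes group collects more hospitalisations per patient, so delay looks harmful. It also contains more patients who stayed alive and on treatment, so delay looks harmless or even favourable in KCCQ summaries that pool visits over follow-up.

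There is also a data-collection gap. Without dates for interruptions after the first dose, a refill a few days late and a gap of several months are recorded alike, and no later analysis plan can recover the difference.

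**Working it through.** The protocol gives no delay rate, exit rate, effect size or sample size calculation, so there is no planned figure to reproduce. What follows is an illustration.

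**Inputs.** From the protocol: 24 months of follow-up with contact every 3 months, hence eight intervals (section 9.2), and the stopping events in section 9.1. Assumed: chance of a new delay per interval q = 5%, 10% or 20%; exit by month 24 of 20% or 40%, constant over time and unrelated to delay.

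**Step 1: chance of being labelled Yes after k intervals,** 1 − (1 − q)^k.

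| q | k = 1 | k = 2 | k = 4 | k = 8 |
|---|---|---|---|---|
| 5% | 5% | 10% | 19% | 34% |
| 10% | 10% | 19% | 34% | 57% |
| 20% | 20% | 36% | 59% | 83% |

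At q = 10%, for example, 1 − 0.9² = 0.19 and 1 − 0.9⁸ = 0.57, a three-fold difference from length of observation alone.

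**Step 2: follow-up by label when delay has no effect.** Exit per interval is e = 1 − (1 − 0.20)^(1/8) = 0.0275 for 20% exit, and 1 − (1 − 0.40)^(1/8) = 0.0619 for 40%. Simulating 400,000 patients gives:

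| Exit by month 24 | q | Mean months, Yes | Mean months, No | Completing, Yes | Completing, No |
|---|---|---|---|---|---|
| 20% | 5% | 23.0 | 21.3 | 87% | 77% |
| 20% | 10% | 22.9 | 20.5 | 87% | 73% |
| 20% | 20% | 22.8 | 18.5 | 85% | 61% |
| 40% | 5% | 21.8 | 18.5 | 73% | 55% |
| 40% | 10% | 21.6 | 17.4 | 72% | 49% |
| 40% | 20% | 21.3 | 14.6 | 69% | 36% |

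Exact check of the second row: a patient is observed for k intervals with probability e(1 − e)^(k−1) for k < 8 and (1 − e)^7 for k = 8, and is still No with probability 0.9^k. Summing 3k months over k gives 21.812 in all, of which 9.753 falls in the No group, whose share is 0.4745. Mean for No = 9.753 / 0.4745 = 20.56; mean for Yes = (21.812 − 9.753) / 0.5255 = 22.95. This agrees with the simulation.

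At an identical monthly admission rate, that row alone gives the Yes group 22.9 / 20.5 = 1.12 times as many admissions per patient.

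**Step 3: other readings of the label.**

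- Delay to first supply only, fixed at the start: 21.8 vs 21.8 months (20% exit) and 19.4 vs 19.4 (40% exit). No artefact.
- 30% of patients with a first-supply delay plus later delays at q = 10%, with 40% exit: 20.6 vs 17.4 months. Smaller than the 21.6 vs 17.4 without first-supply delays, but not gone.
- A gap counts as discontinuation and ends follow-up (20% exit, q = 10%): 11.4 vs 20.6 months. The direction reverses.
- KCCQ at month 24 among completers: everyone has had the same eight intervals, so unequal observation time plays no part.

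**The case against.** In support of the plan, one could fairly say that 9.7.3.2 names neither an outcome nor a time window, that an analysis plan commonly supplies these, and that the study tests no hypothesis and already concedes in section 9.9 that small numbers limit the subgroups. The illustration also rests wholly on assumed rates, and its mildest row shows less than two months' difference. All of this limits the weight of the point. It does not remove it: section 9.1 points to assessment during follow-up, and undated gaps are a matter of data collection that an analysis plan cannot repair.

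Four stronger readings might be inferred, and the protocol does not support them.

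- **That lost exposure goes unmeasured.** The wait for first supply is known in days from two recorded dates, and the adherence device logs doses for patients who have it. Only later gaps lack dates or length, and the device shows them indirectly for its users.
- **That delay is asked only once.** The row lacks the Table 2 mark "Per visits, according to schedule of the study", but so do adherence and hospitalisation, which Table 1 schedules at visits; a glomerular filtration value at diagnosis carries the mark. Sections 9.1 and 9.4 point to repeated collection. Whether the field repeats is unclear.
- **That section 9.1 contradicts itself.** The one-month sentence can be read as covering first supply and the next as covering any supply. Nothing says a shorter wait is not a barrier. The relation is unstated, which is an ambiguity.
- **That the Yes group is certainly enriched for long survivors.** A single assessment at entry would not produce this, and Step 3 shows when it vanishes or reverses.

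**Conclusion.** The point holds conditionally. As written, 9.7.3.2 permits an ever/never grouping built over follow-up, and section 9.1 makes that the natural reading. On that reading, comparisons of cumulative outcomes such as hospitalisation, and of KCCQ summaries over follow-up, are distorted by unequal observation time. Under the assumed rates the spurious difference in mean follow-up runs from 1.7 months (23.0 − 21.3) to 6.7 months (21.3 − 14.6), and is about 2.4 months (22.9 − 20.5) at 10% delay per interval and 20% exit. None of these sizes can be taken from the protocol, and the sign depends on whether a supply gap also counts as discontinuation under 9.3.1, which is not settled. The affected analyses are secondary and descriptive, so this is a change that should be made; it does not undermine the primary description of KCCQ in the whole cohort.

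**What to change.** 1. In 9.7.3.2, define the subgroup by delay to first supply: date of first administration minus date of prescription. State any cut-point in advance, and how a patient with no first administration date is classed.
2. In Tables 1 and 2, record start and end dates of each later gap at the scheduled 3-monthly calls. Analyse these as a time-varying exposure (days without drug before each KCCQ) and per patient-month of follow-up.
3. In 9.1, state how the more-than-one-month wording and the any-delay wording relate, and reconcile both with the discontinuation wording in 9.3.1. Which clinical rule applies is for the sponsor to decide.

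The first change uses dates already collected. The second adds two date fields per gap and makes the interview slightly longer. Gaps before enrolment will rely on recall: patients treated from August 2022 are eligible and data collection starts on 15 November 2023, so recall may reach back about 15 months. Those entries should be identifiable in the data.
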